# **Abbreviations**

AE Adverse Event
AR Adverse Reaction
CI Chief Investigator
CRF Case Report Form
GCP Good Clinical Practice

GDPR General Data Protection Regulation

GP General Practitioner

HRA Health Research Authority
NHS National Health Service

NIHR National Institute for Health Research

PI Principal Investigator

REC Research Ethics Committee

SAE Serious Adverse Event

SAR Serious Adverse Reaction

UK United Kingdom
WP2a Work package 2a
WP2b Work package 2b
WP2c Work package 2c

# 2 Lay Summary

There is strong evidence that sitting for long periods of time can contribute to poor health and wellbeing. In the UK, there are about ~51,000 GPs most of whom are likely to sit for long periods of the day. A typical GP's welcome to a patient is "please take a seat", which has long been seen as an important part of having a good doctor-patient relationship. Studies also suggests that doctors often neglect their own health, and often report low levels of physical activity. Identifying ways to get GPs on their feet and moving more often may be important for their health and to enable them to model good behaviour to their patients. Giving GPs access to a desk that allows them to both sit and stand, whilst working, may help reduce the time they spend sitting during the day, as well as lead to them acting as positive role models in this regard to their patients. Studies have also shown GPs do not regularly have conversations with patients about physical activity; changing to standing consultations may prompt more conversations like this. Here we aim to investigate the practicalities of GPs standing during consultations with their adult patients, and look at whether this is acceptable to both GPs and their patients. We also aim to examine whether having a desks that allows GP to sit or stand changes the amount of time GPs spend sitting each day and whether this has an impact on the amount of physical activity GPs do each day. We are also interested in whether GP's standing has any impact on the relationship between GPs and patients. To do this, we will give GPs a desk that allows them to sit and stand and ask them to use this during consultations with adult patients and during any other time of their day working. We will encourage GPs to stand during as many consultations with their patients as possible and to stand during other working tasks such as administration and doing phone calls. We will measure GPs sitting time and physical activity before getting the workstation and then again when they have the workstation. We will ask patients to complete a brief questionnaire immediately following a consultation where their GP was standing which will explore how they felt about their GP standing. Patients will be asked if they are willing to be contacted at a later date to

take part in a telephone interview which will explore their experiences of standing up with their GP during their consultation. GPs will also be asked to take part in an interview after they have experienced standing consultations to explore their thought and experiences about this and if it had any impact on their relationships with their patients

#### 3 Study background and rationale

Sedentary behaviour accumulated in occupational settings has been specifically associated with an increased risk of type 2 diabetes and all-cause mortality (1), as well as increased risk of musculoskeletal disorders (2), and detrimental work-related engagement and presenteeism (3,4). Furthermore, sedentary behaviour has also been shown to be associated with reduced cognitive function (5), poor mental health (6,7), and a lower quality of life (8). Sedentary behaviour is defined as "any waking behaviour characterized by an energy expenditure ≤1.5 metabolic equivalents, while in a sitting, reclining or lying posture" (9). It has been well documented that office workers spend a large proportion of their working day sitting (10,11), yet data on clinical staff, such as general practitioners (GPs) who are assumed to sit for large proportions of the day, is lacking.

Recent experimental research has shown that breaking prolonged sitting time with regular breaks of standing or movement improves markers of cardiometabolic health (12–14), as well as measures of fatigue and vigour (15,16). Considering this evidence, reducing sedentary behaviour in the workplace may be an important step in improving health, wellbeing and work-related outcomes.

By the nature of their work it is likely that GPs spend large proportions of their working day sitting. This is largely due to their work demands (i.e., consultation time with patients) and their working environment. Unlike other health care workers, GPs work fundamentally revolves around them spending large amounts of time in one place. Therefore, it is important to explore ways in which GPs might be provided with opportunities during their working day to be less sedentary, potentially through the use of height-adjustable workstation in their consultations. Height-adjustable workstations allow the user to alternate between a sitting and standing position to do their work. Not only may this enable GPs to become less sedentary and more physically active, the use of height-adjustable workstations may also help GPs to routinely have conversations with patients about reducing time spent sitting and increasing physical activity levels to improve their health. This is particularly important as large proportions of the general population are insufficiently active and spend long periods of time sitting, typically between 9 and 10 hours per day (17). This issue is compounded by the fact that GPs do not regularly discuss physical activity with patients (18).

For most people, their GP is the first port of call for health advice, so primary care is an ideal place in which to promote physical activity and discourage high levels of sitting in the population.

Whilst standing in healthcare settings is not new, for example, ward rounds in hospital are typically conducted with doctors standing and patients sitting, this is not currently the case in primary care. GP consultations historically have been conducted sitting down. Introducing standing in consultations

V 1.1 Date: 12/03/2021 IRAS: 288859

would be a large cultural and environmental shift/change for patients and GPs. However, current evidence puts particular prominence on the use of environmental restructuring as a behaviour change technique in interventions aiming to reduce occupational sitting time (19), with 50% of interventions designed to reduced sitting time in adults having added objects to the environment (19). Environmental restructuring in this instance is the introduction of height-adjustable workstations. Due to the nature of GPs work, this is a setting that, in theory, height-adjustable workstations could be of benefit to both GPs and patients.

A recent study that investigated the effect of implementing height-adjustable workstations among office workers within the National Health Service (NHS), alongside other behaviour change techniques such as education and self-monitoring, reduced occupational sitting by over 80 minutes per day when compared with the control group (20). Along with this large reduction in sitting, significant improvements were also observed for job performance, work engagement, occupational fatigue, sickness presenteeism, daily anxiety, and quality of life (20). It is now of interest to examine different clinical/work settings that may benefit from sitting less and standing more, using height-adjustable workstations to facilitate this. Due to the nature of GPs work, this is a setting that, in theory, height-adjustable workstations could facilitate this change and be of benefit to both GPs and patients. However, before implementing height-adjustable workstations widely within general practice, it is important to consider how feasible and acceptable this form of intervention may be to GPs and patients alike.

# 4 Aims and objectives

# 4.1 Primary objective

To investigate the feasibility and acceptability to GPs and patients of GPs standing during consultations in primary care.

# 4.2 Secondary objectives

- 1. Assess the doctor-patient relationship when GPs stand during consultations.
- 2. Assess patients views of standing during their GP consultation.
- 3. Assess GPs self-reported use of standing workstations during a variety of working tasks.
- 4. Assess device-based measurement of GPs use of the workstation.
- 5. Derive preliminary estimates of the effect of the intervention on GPs total daily sitting time and physical activity, both in work and outside of work.
- 6. Establish and refine a study recruitment strategy for GPs and patients.
- 7. Determine attrition in the trial (GPs).
- 8. If possible, assess whether there are any differences in trial recruitment, retention and acceptability between ethnic groups, gender and practice location for GPs.

V 1.1 Date: 12/03/2021 IRAS: 288859

 Assess the acceptability of measurement instruments to GPs and patients, including the activPAL inclinometer as the tool for the measurement of sitting time and physical activity in GPs.

- 10. Assess intervention fidelity.
- 11. Estimate the standard deviation of sitting time to inform a sample size calculation for a potential phase III RCT.

#### 5 Study design and population

The study forms part of a wider programme of research where work package 1 involved a survey to assess GPs views of using height-adjustable workstations during their working day. Preliminary results from this study showed 61% of GPs wanted to have a height-adjustable workstation in their consultation room, and 64% of GPs thought these workstations could be used during face-to-face consultations. The current study adopts a pre-post single group mixed methods design and is divided into three work packages; work package 2a (WP2a: experimental study to test the feasibility and acceptable of GPs standing during consultations), work package 2b (WP2b: patient consultation exit questionnaires) and work package 2c (WP2c: patient interviews about their experiences of their GP standing during consultations). Each work package will be outlined below, with specific reference to the relevant work package when applicable. This study will include GPs and their patients and both have their own participation inclusion and exclusion criteria. These are as follows.

#### 5.1 Inclusion criteria

GPs will be considered eligible if they meet the following criteria:

- Currently working as a GP in the UK.
- Working at least five clinical sessions a week.

Patients will be considered eligible if they meet the following criteria:

- ≥ 18 years of age.
- Attended a consultation with a GP who was standing as part of their participation in the upSTANDing GP study.

# 5.2 Exclusion criteria

GPs may not enter the study if ANY of the following apply:

- Medical student who is not yet qualified as a GP and any other health care professional.
- Pre-existing condition that inhibits an individual's ability to stand or to be physically activity.

Patients may not enter the study if ANY of the following apply:

• Unable to communicate in English and unable to provide written informed consent.

#### 5.3 Sample size

As this is a feasibility trial a formal sample size calculation has not been conducted. The research has not been designed or powered to detect a statistically significant difference in efficacy between time

points. Sample sizes of between 24 and at least 70 participants have been recommended (21,22). A recruitment target of between 30 and 40 GPs, of between 200 and 300 patients (completing the exit questionnaire) has been set. It is anticipated that between 20-25 patients will participate in a semi-structured interview (WP2c).

# 6 Participant Flow

In this study, participants will be classified into two categories (GPs and patients and as described above in section 5). Here, the respective timelines for both GPs and patients progression through the study are outlined.

[figure not shown]

Figure One: Flow diagram for GP study (WP2a)

All activities here will be conducted by the research team

[figure not shown]

Figure Two. Flow diagram of patient participants (WP2b and WP2c)

# 7 Purpose, Context and Rationale

We plan to implement height-adjustable workstations (also known as a sit-stand desks or standing desks), which allow GPs to switch, within a few seconds, between sitting and standing positions during their working day. Height-adjustable workstations have formed a major role in interventions to reduce occupational sitting (20), and given the sedentary nature of GPs working lives and the role they play in modelling positive behaviour to their patients, it is of interest to test whether using height-adjustable workstation to facilitate less sitting and more standing, is feasible and acceptable within general practice.

# 7.1 Height-adjustable workstations

Height-adjustable workstations allow the user to switch, in a few seconds, between a sitting and standing position by adjusting the high of the workstation. All GPs will be shown how to use the workstation correctly (they will also receive a leaflet explaining how to use the workstation) and will be asked to use the workstation during consultations (face-to-face, online and telephone) and whenever else they wish to do so (i.e. whilst doing administrative duties). It will be GPs and patient's

decision when to use the workstation in the standing position. Patients will not be forced to stand if they do not wish to, even if the GP is standing.

# 8 Procedures for GPs (WP2a)

#### 8.1 Recruitment

GPs will be recruited through the West Midlands CRN and through existing partnerships and links. Where possible, GPs will be recruited from a diverse range of practices (i.e. those serving geographical areas of high a low deprivation), to ensure where possible that a broad sample of GPs in terms of sex, age and ethnicity participate in this research.

# 8.2 Screening

GPs will be screened using the inclusion and exclusion criteria outlined above in Section 5 via telephone, email or a face-to-face meeting.

# 8.3 Informed consent (GPs)

GPs written or verbal informed consent will be obtained at the start of the baseline assessment. It may be necessary to conduct the baseline assessment remotely due to COVID-19, in this event verbal informed consent will be obtained. Verbal informed consent will be audio recorded on an encrypted dictaphone and stored in accordance with the procedures outline in Section 10. Where verbal consent it taken, each of the statements on the written consent form will be read out and GPs will be asked to verbally indicate their agreement (or not) with each statement. This will be audio recorded. The researcher will then sign and date the written consent form and then provide the GP with a copy after the assessment. Each GP will have been provided with a participant information sheet and the activPAL instructions at least 24 hours prior to providing consent to participate. Where verbal consent is taken it will be documented on the consent form and stored as defined in Section 10.

# 8.4 Baseline assessment (GPs)

Once GPs have provided written or verbal informed consent, data collection will commence. Details in relation to this are outlined below in *Baseline and follow-up data collection (Section 8.6)*. It is from the point of the baseline assessment that all other study related activities are outlined and the timings are set.

#### 8.5 Height-adjustable desk Intervention

Figure Three shows a logic model that explains how the activities of the intervention are expected to contribute to particular results. The workstation will be delivered to the GP practice by a member of the research team no less than eight days after baseline. Once there, the workstation will be installed in GPs consultation room. The researcher will explain to the GP how to correctly use the workstation and will remind the GP of the purpose of the workstation (to reduce sitting time at work and role model

V 1.1 Date: 12/03/2021 IRAS: 288859

good behaviour for patients). GPs will be reminded that the height-adjustable workstation should not be used with patients under 18 years and should only be used during consultations with adults, telephone/video consultations and during administration tasks. The height-adjustable workstation will be removed four weeks after installation. Any time taken as holiday or leave of absence will be added at the end to ensure four weeks use of the workstation. See Appendix A for an example of the height-adjustable workstation that will be used in this study.

[figure not shown]

Figure Three: Logic Model

#### 8.6 Baseline and follow-up data collection

#### 8.6.1 activPAL (sitting time)

GPs will be asked to wear an activPAL micro monitor on their thigh for 24 hours a day for up to eight days at two different time periods; from baseline for up to eight days (baseline period) and for the last eight days of the four week height-adjustable workstation intervention (follow-up). The activPAL device, which is about 4cm by 2cm, will be attached to the thigh using a hypoallergenic waterproof dressing (Hypafix Transparent). The device is waterproofed by a nitrile sleeve and wrapped in a waterproof dressing (Hypafix Transparent). GPs will be asked to complete a wear log on each day that they are wearing the activPAL detailing the time they woke up and the time they fell asleep. GPs will also record the time they started and finished work on a given day which will allow data to examined for work and out of work respectively. The activPAL has been found to be a valid and reliable device for measuring time spent sitting, standing and stepping, as well as number of postural transitions in adult populations (23).

8.6.2 GP questionnaires (experiences of using the height-adjustable worstation at work) GPs will be asked to complete two sets of questionnaires, one at baseline (or at workstation installation) and one at workstation removal (follow up). These questionnaires will examine the following at baseline:

- How often GPs discussed physical activity/exercise, sedentary behaviour/sitting, standing and sleep with their patients.
- Their views on using height-adjustable workstations for face-to-face consultations with ablebodied adults, telephone consultations with adults, video consultations with adults and administration tasks.
- How their patients are alerted that they are ready to be seen by them for a face-to-face consultation.
- What their preferred posture (sitting, standing or don't mind) is during face-to-face
  consultations with able-bodied adults also standing, during face-to-face consultations with
  able-bodied adults sitting, video consultations with adult patients, telephone consultations with
  adult patients and during administration tasks.

The follow-up questionnaire will include the same questions as baseline, with the following additions:

- Has the workstation been used in the past four weeks, if no why not?
- · How often the workstation has been used.
- What prompted its use.
- Did the desk make the GP feel self-conscious?
- Was the desk obtrusive?
- How often they stood for face-to-face consultations.

V 1.1 Date: 12/03/2021 IRAS: 288859

 Did standing prompt conversations with patients about physical activity/exercise, sedentary behaviour/sitting, standing or sleep.

- Was the doctor-patient relationship affected by standing during consultations.
- Was the GPs ability to listen to patients affected by standing during consultations.
- Were patients understanding of the issues discussed affected by standing during the consultation.
- Were there any consultations where it was always better to sit or better to stand?
- Whether the GP explained, or the patient asked by they were standing.
- Did standing impact the length of consultations.
- Did they use the desk more often during different periods of the day?
- What tasks was the desk used for?
- Did the workstation make the GP think more about the time they spend sitting at work and at home?

These questionnaires can be completed online or on paper. Online questionnaires will be completed via Qualtrics.

#### 8.6.3 Device measurement of workstation use

Each workstation will be fitted with a device that measures the GPs use of the desk. The measures include; frequency of position change (from sitting to standing and vice versa), time the workstation is in the sitting position and standing position and maximum time the desk was in a certain position before a change.

#### 8.7 Interviews with GPs

GPs will be invited to take part in an interview, which will take place after the removal of the height-adjustable workstation. Interviews can take place face-to-face or remotely via telephone or online conferencing software. Interviews with GPs will be semi-structured and they will be asked about their experiences using a height-adjustable workstation during consultations, and during other work-related tasks. They will be asked about the impact using the workstation had on the doctor-patient relationship, how acceptable they found the workstation, their perception of the long-term feasibility of implementing such workstations and on their perception of patients' views of the height-adjustable workstation. GPs will also be asked if they felt using the workstation had any effect on their own behaviour in both work and home settings (time spent sitting, standing, moving and sleeping), their own health (mental and physical) and their own work-related outcomes (productivity, efficiency etc). Data from the interviews will be audio-recorded using an encrypted dictaphone and transcribed, summarised and coded by a Loughborough University approved commercial company (JC Porter, using the methods described and outlined in *Data Management* below).

# 9 Procedures for Patients (WP2b and WP2c)

Here, procedures are described for WP2b (exit questionnaire) and WP2c (patient interviews). When procedures differ between WP2b and WP2c, this is made clear in the headings and in text where appropriate.

# 9.1 Recruitment

Patients will be recruited for both WP2b and WP2c following exit from their GP consultation.

# 9.2 Consultation exit questionnaires with patients (WP2b)

GPs will consider the inclusion and exclusion criteria outlined above in Section 5.1 and 5.2, and if the patient is considered to have met the study criteria the GP will give the patient an exit questionnaire to complete at the end of the consultation. GPs will only ask patients to complete the exit questionnaire if it is appropriate to so do. We also plan to have provision for researchers to approach patients at the end of the consultation to administer exit questionnaire outside of the consultation room; where this is the case the GP will give the patients a green card to indicate to the researcher it is appropriate for the researcher to approach the patients. If no card is issued the researcher will not approach the patient. We are only interested in patients who experienced a standing consultation.

Patient written informed consent will be obtained at the start of the exit questionnaire and prior to them completing the exit questionnaire detailed above. This process is the same regardless of whether the questionnaires are patient completed or researcher administered. Additional written consent will be sought from patients who are willing to be contacted to take part in a later follow-up interview study (WP2c) about their views on the GP using a height adjustable desk during their consultation. Patients do not need to provide and identifiable data on the exit questionnaire unless they wish to take part in a follow-up interview about their views of standing during their GP consultation.

Once patients have given their written informed consent, they will be able to complete the questionnaire relating to the consultation they have just had with their GP. The questionnaire will focus on the experience of patients during these consultations and the potential impact of their GPs standing during their consultations on the doctor-patient relationship, GPs listening skills and patients' ability to understand the issues discussed. Questions will ask about what posture the patient adopted during the consultation (sitting, standing or a combination), what preference, if any the patient has regarding their GPs adopted posture, whether the GP discussed physical activity, exercise, sitting/sedentary behaviour, standing or sleep with them, and whether the consultation made them think more about the time they spend sitting. Patients will also be asked brief questions about themselves (age group, gender, ethnicity and employment status), how often they visit their GP per year and whether their consultation was for a few specific medical conditions which GPs are more likely to discuss physical activity (weight management/maintenance, type 2 diabetes, cardiovascular

disease, high blood pressure, mental health or musculoskeletal health). There will also be time for the patient to make additional comments about their experience of the standing during their consultation.

Completed questionnaires will either be placed in a secure box at the practice reception, handed to a member of practice reception staff, handed back to the researcher if present or returned to the research team using a freepost envelope. The method of returning the questionnaires will be discussed with each practice and a decision will be made to ensure the needs of that practice are met. If questionnaires are left at the practice, a member of the research team will collect these when convenient. If response rates are poor, these questionnaires can be asked in person immediately following the patients consultation by a member of the research team. If conducted in person, all necessary COVID-19 protocols will be adopted to ensure safety for the patient and researcher.

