# 10.1.2 Questionnaire and activPAL data

All questionnaire and activPAL data for GPs will not contain identifiable information but will be allocated an identification number which will be stored securely at Loughborough University. Patient exit questionnaires may contain identifiable information if they consent to provide contact information for the interviews. Anonymous research data will be stored on the University's secure server for 10 years after the completion.

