# 12.1 Data Management

All research data relating to WP2b will be anonymous unless participants wish to disclose their personal details. All personal data gathered will be detached from research data and will be stored separately at Loughborough University. Continued consent to store contact details for future research will be taken from participants prior to research activities. Loughborough University is the custodian of the data and therefore both electronic and paper-based data will be stored on the University's Secure Servers in line with the University's Privacy Statement. Loughborough University are the data controllers for the study and have completed a Data Protection Impact Assessment. The transcription company are data processors, are compliant with General Data Protection Regulations (GDPR) guidance and have a confidentiality agreement in place with Loughborough University.

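### Exit questionnaires may go back through the GP's own reception staff with no sealing required, and may be self-completed or researcher-asked with no record of which, so patient acceptability answers may lean favourable

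*Protocol*

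**What the plan says.** Section 9.2 describes the exit questionnaire. It covers the possible impact of the GP's standing on the doctor-patient relationship, the GP's listening and the patient's understanding, along with posture preference and topics discussed.

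- **Consent.** "Patient written informed consent will be obtained at the start of the exit questionnaire and prior to them completing the exit questionnaire detailed above". This applies whether the patient or a researcher completes the form.
- **Contact details.** Section 10.1.2 adds: "Patient exit questionnaires may contain identifiable information if they consent to provide contact information for the interviews". Section 12.1 states: "All research data relating to WP2b will be anonymous unless participants wish to disclose their personal details".
- **Return.** There are four routes: a secure box at reception, the researcher if present, freepost, or the form is "handed to a member of practice reception staff". The choice is local: "The method of returning the questionnaires will be discussed with each practice and a decision will be made to ensure the needs of that practice". As to timing: "If questionnaires are left at the practice, a member of the research team will collect these when convenient".
- **Mode.** Self-completion is one mode. The other is researcher administration, which appears twice. It is a general provision ("We also plan to have provision for researchers to approach patients at the end of the consultation to administer exit questionnaire outside of the consultation"), for patients to whom the GP has given a green card. It is also a fallback: "If response rates are poor, these questionnaires can be asked in person immediately following the patients consultation by a member of the research team".

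Section 10.1.1 says that identifiers on the form are recorded and then taken off it, without saying when or by whom.

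**The concern.** Patients are asked, straight after seeing their GP, whether standing harmed the consultation. A patient who must hand the form to that GP's staff, possibly with a signature or telephone number on it, has a reason to soften a critical answer. So does a patient questioned face to face. These items serve the patient side of the primary objective (section 4.1) and secondary objectives 1 and 2 (section 4.2).

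The second issue is traceability. Two modes and four return routes are allowed, and the protocol does not require either to be noted on the form. If they are not captured at collection, no later analysis, however well planned, can examine their influence. That makes it a matter for the protocol and not only for an analysis plan.

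**Working it through.** The protocol gives no calculated figure on this point, and section 5.3 states that no formal sample size calculation was done. There is nothing to reproduce. The check is a reading of the text, followed by an illustration of scale.

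**Reading the text**

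1. *Is the reception route protected?* The secure box and freepost are alternatives to reception, not conditions on it. No sealing step is described for a form handed over, and forms may wait at the practice for an unspecified time. Section 10.1.1 removes identifiers, but describes no removal before reception handles the form.
2. *What identifies the patient?* Every form opens with written consent. Contact details are needed only from patients willing to be interviewed (sections 9.2 and 10.1.1). The protocol does not say what the consent entry shows.
3. *What is tied to practice?* The return route is, because it is agreed with each practice. The mode need not be. The fallback gives no threshold, denominator or unit for a poor response rate. If it is applied practice by practice, mode follows practice. If it is applied across the study, mode follows calendar time. The general provision allows researcher administration with no trigger at all.
4. *Is mode or route recorded?* No section requires it.

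**Scale, on assumed values only**

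Inputs from section 5.3: 200 to 300 patients and 30 to 40 GPs, so 200/40 = 5 to 300/30 = 10 forms per GP. Assumed, because the protocol gives none of them: true acceptability of 50% to 80%; intracluster correlation (ICC) within GP of 0 to 0.10; answers 5, 10 or 15 points more favourable when asked in person; 25% to 75% of forms asked in person.

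Sampling error: 95% half-width = 1.96 × √(p(1−p) × DE / n), with DE = 1 + (m−1) × ICC and m = forms per GP.

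- No clustering, p = 0.8, n = 300: 1.96 × √(0.16/300) = 4.5 points.
- No clustering, p = 0.5, n = 200: 1.96 × √(0.25/200) = 6.9 points.
- ICC 0.10, p = 0.8, n = 300, 40 GPs: m = 7.5, DE = 1.65, half-width 5.8 points.
- ICC 0.10, p = 0.5, n = 200, 30 GPs: m = 6.67, DE = 1.57, half-width 8.7 points.

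Shift in the pooled percentage, relative to all forms being self-completed = share asked in person × mode effect:

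| Mode effect | 25% in person | 50% | 75% |
|---|---|---|---|
| 5 points | 1.25 | 2.5 | 3.75 |
| 10 points | 2.5 | 5.0 | 7.5 |
| 15 points | 3.75 | 7.5 | 11.25 |

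A 5-point effect stays below every half-width shown. A 10-point effect can reach the same size as sampling error, and a 15-point effect can exceed it. The documents do not say which row applies. Unlike sampling error, such a shift does not shrink as more patients are recruited.

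**The case against.** The other side has several good points.

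- *A reader might infer that mode is chosen per practice because of poor response.* The text does not say so. Only the return route is decided per practice, the trigger has no stated unit, and researcher administration is also planned without it. A poor response rate is also not a poor rating, so mode is not selected on the answers. This stands.
- *A reader might infer that consent on the form contradicts anonymity in section 12.1.* That section carries its own exception for patients who choose to disclose details, and nothing says the consent entry bears a name. The identifiability problem in transit is clear for interview volunteers and uncertain for the rest. This stands.
- *A reader might call these ratings of the patient's own GP.* The questions concern the effect of the GP's standing, which is less personal. This stands and tempers the expected courtesy bias.
- *No comparison of patient ratings between practices is planned.* Secondary objective 8 concerns GPs only, section 10.2 says analyses will be mainly descriptive, and the protocol sets no acceptability threshold that a shift could cross. This stands and limits the consequence to the pooled description.
- *Asking in person counters non-response, which itself threatens acceptability data.* True, so a ban on it would trade one bias for another.
- *Envelopes and tick-boxes are form design, and reporting by mode belongs in an analysis plan.* Partly true. But section 9.2 itself lists reception staff as a route and allows two modes, so the safeguard belongs beside them.

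**Conclusion.** The point holds in limited form. Section 9.2 allows a form that begins with consent, and for some patients carries contact details, to pass through the GP's own reception with no sealing required. It allows two modes with no record of which was used. This may make answers on the patient side of the primary objective more favourable. The direction is a reasonable inference, not something the protocol shows. The size cannot be estimated from the documents. On the assumed ranges above, the pooled shift runs from 1.25 to 11.25 points against half-widths of 4.5 to 8.7, so it could be negligible or comparable to sampling error.

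The documents do not support saying that mode is confounded with practice, that anonymity is breached for all respondents, or that a planned between-practice comparison is spoiled. What they do support is a change to section 9.2 that should be made before data collection, because route and mode may not be recoverable afterwards.

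**What to change.** Amend section 9.2 as follows.

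1. Any form left at the practice goes in an envelope sealed by the patient, or into the secure box, or by freepost. Reception staff receive only sealed envelopes.
2. Consent and contact details go on a detachable slip that shares a serial number with the questionnaire and is returned separately. Section 10.1.1, which keeps consent with the raw data, needs matching wording.
3. Each form records its return route and whether it was self-completed or asked by a researcher.
4. Acceptability results are reported by mode. This shows the reader how answers differ. It will not separate mode from practice or time if the two coincide completely.
5. In-person administration stays as an option against non-response, but where a researcher is present the preference is to hand out and collect a self-completed form. State the denominator, threshold and unit (practice or whole study) for a poor response rate.

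The cost is stationery, slightly more data handling to link slips to forms, and a few sentences of protocol text.
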